## **7. TREATMENT**

Study treatment is defined as any investigational treatment(s), marketed product(s), placebo or medical device intended to be administered to a study participant according to the study randomization or treatment allocation

Study treatment includes both Investigational [Medicinal] Product (IP/IMP) and Non-investigational [Medicinal] Product (Non-IP/Non-IMP) and can consist of the following:

- Nivolumab

An investigational product, also known as investigational medicinal product in some regions, is defined a pharmaceutical form of an active substance or placebo being tested or used as a reference in a clinical study, including products already with a marketing authorization but used or assembled (formulated or packaged) differently than the authorized form, or used for an unauthorized indication, or when used to gain further information about the authorized form.

Other medications used as support or escape medication for preventative, diagnostic, or therapeutic reasons, as components of the standard of care for a given diagnosis, may be considered as non-investigational products.

Table 7.-1: Study treatments for CA209923					
Product Description / Class and Dosage Form	Potency	IP/ Non-IMP	Blinded or Open Label	Packaging / Appearance	Storage Conditions (per label)
Nivolumab Solution for Injection	100 mg (10 mg/mL) and 40 mg (10 mg/mL)	IP	Open label a	Clear to opalescent colorless to pale yellow liquid. May contain particles. 240 mg kit contains: 2 x 100 mg vials (10 mL/vial) and 1 x 40 mg vial (4 mL/vial) or carton containing 5 vials of 100 mg (10 mL/vial)	2 to 8°C. Protect from light and freezing

May be labelled as either ‘BMS-936558-01’ or ‘Nivolumab’.

a The term ‘Open label’ refers to the medication as it is upon receipt at the pharmacy (unblinded pharmacist). Trial design and conduct are double-blind.

## 7.1 Treatments Administered

The selection and timing of dose for each participant is as follows:

**Table 7.1-1: Selection and Timing of Dose**

Study Treatment	Unit dose strength(s)	Dosage formulation Frequency of Administration	Route of Administration
BMS-936558-01 (nivolumab) 480 mg or 960 mg	100 mg (10 mg/mL) and 40 mg (10 mg/mL) sterile solution	Single dose infusion	Intravenous

Participants are randomized to receive double-blind nivolumab at a dose of 480 mg or 960 mg as a 90 minute infusion on Day 1.

Infusions will be prepared by an unblinded pharmacist according to a pharmacy manual, provided separately. The infusion volume for the two treatment groups will be the same, to preserve the blind.

Participants should be carefully monitored for infusion reactions during nivolumab administration. Nivolumab contains only human immunoglobulin protein sequences, therefore it is unlikely to be immunogenic and induce infusion or hypersensitivity reactions. However, if such a reaction were to occur, it might manifest with fever, chills, rigors, headache, rash, pruritus, arthralgias, hypotension, hypertension, bronchospasm, or other allergic-like reactions. All Grade 3 or 4 infusion reactions should be reported within 24 hours to the study medical monitor and reported as an SAE if it meets the criteria. Infusion reactions should be graded according to CTCAE (Version 4) guidelines.

**Treatment recommendations are provided below and may be modified based on local treatment standards and guidelines, as appropriate:**

For Grade 1 symptoms: (mild reaction; infusion interruption not indicated; intervention not indicated):

- Remain at bedside and monitor participant until recovery from symptoms.

For Grade 2 symptoms: (moderate reaction requiring infusion interruption but responds promptly to symptomatic treatment [eg, antihistamines, non-steroidal anti-inflammatory drugs, narcotics, corticosteroids, bronchodilators, IV fluids]):

- Stop the nivolumab infusion, begin an IV infusion of normal saline, and treat the participant with diphenhydramine 50 mg IV (or equivalent) and/or acetaminophen/paracetamol 325 to 1000 mg; remain at bedside and monitor participant until resolution of symptoms. Corticosteroid and/or bronchodilator therapy may also be administered as appropriate. If the infusion is interrupted, then restart the infusion at 50% of the original infusion rate when symptoms resolve; if no further complications ensue after 30 minutes, the rate may be increased to 100% of the original infusion rate. Monitor participant closely. If symptoms recur, then no further nivolumab will be administered.

For Grade 3 or 4 symptoms: (Grade 3: severe reaction: prolonged symptoms [e.g., not rapidly responsive to symptomatic medication and/or brief interruption of infusion] or recurrence of symptoms following initial improvement; Grade 4: Life-threatening; pressor or ventilatory support indicated):

- Immediately discontinue infusion of nivolumab. Begin an IV infusion of normal saline and treat the participant as follows: Recommend bronchodilators, epinephrine 0.2 to 1 mg of a 1:1000 solution for subcutaneous administration or 0.1 to 0.25 mg of a 1:10,000 solution injected slowly for IV administration, and/or diphenhydramine 50 mg IV with methylprednisolone 100 mg IV (or equivalent), as needed. Participant should be monitored until the Investigator is comfortable that the symptoms will not recur. Nivolumab will be permanently discontinued. Investigators should follow their institutional guidelines for the treatment of anaphylaxis. Remain at bedside and monitor participant until recovery from the symptoms.

For late-occurring hypersensitivity symptoms: (eg, appearance of a localized or generalized pruritus within 1 week after treatment) symptomatic treatment may be given (e.g., oral antihistamine or corticosteroids).

## **7.2 Method of Treatment Assignment**

Study using Interactive Response Technology (IRT): All participants will be centrally randomized using an Interactive Response Technology (IRT). Before the study is initiated, each user will receive log in information and directions on how to access the IRT.

Study treatment will be dispensed at the study visits as listed in Schedule of Activities ([Section 2](#)).

Enrolled participants, including those not dosed, will be assigned sequential participant numbers comprised of the site number and a unique participant identifier. Those enrolled participants meeting inclusion and exclusion criteria will be eligible to be randomized. Randomization numbers will be assigned prior to dosing.

During the screening visit, the investigative site will contact the Interactive Response Technology (IRT) system to assign the participant identification number. Once it is determined that the participant meets the eligibility criteria following the screening visit, the investigative site will call the IRT to randomize the participant into the open dose panel.

## **7.3 Blinding**

Blinding of treatment assignment is critical to the integrity of this clinical study. However, in the event of a medical emergency or pregnancy in an individual participant in which knowledge of the investigational product is critical to the participant's management, the blind for that participant may be broken by the investigator. The participant's safety takes priority over any other considerations in determining if a treatment assignment should be unblinded.

Before breaking the blind of an individual participant's treatment, the investigator should determine that the unblinded information is necessary, i.e., that it will alter the participant's

immediate management. In many cases, particularly when the emergency is clearly not related to the investigational product, the problem may be properly managed by assuming that the participant is receiving active product. It is highly desirable that the decision to unblind treatment assignment be discussed with the Medical Monitor, but the investigator always has ultimate authority for the decision to unblind. The Principal Investigator should only call in for emergency unblinding AFTER the decision to discontinue the participant has been made.

For this study, the method of unblinding for emergency purposes is IRT.

In cases of accidental unblinding, contact the Medical Monitor and ensure every attempt is made to preserve the blind.

Any request to unblind a participant for non-emergency purposes should be discussed with the Medical Monitor.

In case of an emergency, the investigator(s) has unrestricted access to randomization information via the Interactive Response Technology (IRT) and is capable of breaking the blind through the IRT system without prior approval from sponsor. Following the unblinding the Investigator shall notify the medical monitor and/or study director. For information on how to unblind in an emergency, consult the IRT manual.

Study participants and all clinical research site personnel, except the pharmacist, will be blinded. The pharmacist at the site and/or designee will be unblinded to the randomized treatment assignments in order to dispense treatment from bulk supplies, as needed.

Members of BMS Research and Development and their designees will be unblinded to study treatments to facilitate real-time analyses of PK, RO, and safety data in support of dose selection for future studies. No unblinded data will be communicated to Investigators. This unblinding is not expected to affect the integrity of the trial. PK endpoints are objective assessments that should not be affected by unblinding.

#### **7.4 Dosage Modification**

Not applicable.

#### **7.5 Preparation/Handling/Storage/Accountability**

The investigational product should be stored in a secure area according to local regulations. It is the responsibility of the investigator to ensure that investigational product is only dispensed to study Participants. The investigational product must be dispensed only from official study sites by authorized personnel according to local regulations.

The product storage manager should ensure that the study treatment is stored in accordance with the environmental conditions (temperature, light, and humidity) as determined by BMS. If concerns regarding the quality or appearance of the study treatment arise, the study treatment should not be dispensed and contact BMS immediately.

Study treatment not supplied by BMS will be stored in accordance with the package insert.

Investigational product documentation (whether supplied by BMS or not) must be maintained that includes all processes required to ensure drug is accurately administered. This includes documentation of drug storage, administration and, as applicable, storage temperatures, reconstitution, and use of required processes (e.g., required diluents, administration sets).

Participants should be carefully monitored for infusion reactions during nivolumab administration. Infusion of nivolumab may be interrupted or discontinued depending on how well the participant tolerates the treatment. If an acute infusion reaction is noted, participants should be managed according to [Section 7.1](#).

Nivolumab Injection, 100 mg/10 mL (10 mg/mL) and 40 mg/mL (10 mg/mL) Nivolumab injection is to be administered as an IV infusion through a 0.2-micron to 1.2-micron pore size, low-protein binding in-line filter at the protocol-specified doses. It is not to be administered as an IV push or bolus injection. Nivolumab injection can be infused undiluted (10 mg/mL) or diluted with 0.9% Sodium Chloride Injection, USP or 5% Dextrose Injection, USP to protein concentrations as low as 0.35 mg/mL. Instructions for dilution and infusion of nivolumab injection may be provided in the clinical protocol, pharmacy binder, or pharmacy reference sheet. Care must be taken to assure sterility of the prepared solution as the product does not contain any antimicrobial preservative or bacteriostatic agent. Infusion-related supplies (eg. IV bags, in-line filters, 0.9% NaCl solution) will not be provided by the Sponsor and should be purchased locally if permitted by local regulations.

No incompatibilities have been observed between nivolumab injection and polyvinyl chloride (PVC), non-PVC/non-DEHP (di(2-ethylhexyl)phthalate) IV components, or glass bottles have been observed.

Further guidance and information for final disposition of unused study treatment are provided in [Appendix 2](#).

## **7.6 Retained Samples for Bioavailability / Bioequivalence**

Not applicable.

## **7.7 Treatment Compliance**

Study drug will be administered in the clinical facility. Treatment compliance will be monitored by drug accountability and eCRF.

## **7.8 Concomitant Therapy**

### **7.8.1 Prohibited and/or Restricted Treatments**

Prohibited and/or restricted medications taken prior to study treatment administration or during the study are described below. Medications administered during the index hospitalization within

1 week prior to study treatment administration must be recorded on the CRF. Any concomitant therapies must be recorded on the CRF.

- 1) During the study, immunosuppressive agents are prohibited unless utilized to treat a drug related adverse event. **NOTE:** Adrenal replacement steroid doses up to the equivalent of hydrocortisone 300 mg/day for the treatment of septic shock are permitted.

### **7.8.2 Other Restrictions and Precautions**

Not applicable.

## **7.9 Treatment After the End of the Study**

At the end of the study, BMS will not continue to provide BMS supplied study treatment to participants/investigators unless BMS chooses to extend the study. The investigator should ensure that the participant receives appropriate standard of care to treat the condition under study.

## **8. DISCONTINUATION CRITERIA**

### **8.1 Discontinuation from Study Treatment**

Participants **MUST** discontinue investigational product (and non-investigational product at the discretion of the investigator) for any of the following reasons:

- Participant's request to stop study treatment. Participants who request to discontinue study treatment will remain in the study and must continue to be followed for protocol-specified follow-up procedures. The only exception to this is when a participant specifically withdraws consent for any further contact with him/her or persons previously authorized by participant to provide this information.
- Any clinical adverse event (AE), laboratory abnormality or intercurrent illness which, in the opinion of the investigator, indicates that continued participation in the study is not in the best interest of the participant
- Termination of the study by Bristol-Myers Squibb (BMS)
- Loss of ability to freely provide consent through imprisonment or involuntarily incarceration for treatment of either a psychiatric or physical illness

Discontinuation of the study treatment for abnormal liver tests should be considered by the investigator when a participant meets one of the conditions outlined [Section 9.2.8](#) or if the investigator believes that it is in best interest of the participant.

Refer to the Schedule of Activities for data to be collected at the time of treatment discontinuation and follow-up and for any further evaluations that can be completed

In the case of pregnancy, the investigator must immediately notify the BMS Medical Monitor/designee of this event. Please call the BMS Medical Monitor/designee within 24 hours of awareness of the pregnancy. See [Section 9.2.6](#) for additional details.

All participants who discontinue study treatment should comply with protocol specified follow-up procedures as outlined in [Section 2](#). The only exception to this requirement is when a participant withdraws consent for all study procedures including post-treatment study follow-up or loses the ability to consent freely (i.e., is imprisoned or involuntarily incarcerated for the treatment of either a psychiatric or physical illness).

If study treatment is discontinued prior to the participant's completion of the study, the reason for the discontinuation must be documented in the participant's medical records and entered on the appropriate case report form (CRF) page.

### **8.1.1 Post Study Treatment Study Follow-up**

Participants who discontinue study treatment may continue to be followed.

## **8.2 Discontinuation from the Study**

Participants who request to discontinue study treatment will remain in the study and must continue to be followed for protocol-specified follow-up procedures. The only exception to this is when a participant specifically withdraws consent for any further contact with him/her or persons previously authorized by participant to provide this information.

- Participants should notify the investigator of the decision to withdraw consent from future follow-up **in writing**, whenever possible.
- The withdrawal of consent should be explained in detail in the medical records by the investigator, as to whether the withdrawal is from further treatment with study treatment only or also from study procedures and/or post treatment study follow-up, and entered on the appropriate CRF page.
- In the event that vital status (whether the participant is alive or dead) is being measured, publicly available information should be used to determine vital status only as appropriately directed in accordance with local law.
- If the participant withdraws consent for disclosure of future information, the sponsor may retain and continue to use any data collected before such a withdrawal of consent.

## **8.3 Lost to Follow-Up**

- All reasonable efforts must be made to locate participants to determine and report their ongoing status. This includes follow-up with persons authorized by the participant.
- Lost to follow-up is defined by the inability to reach the participant after a minimum of **three** documented phone calls, faxes, or emails as well as lack of response by participant to one registered mail letter. All attempts should be documented in the participant's medical records.
- If it is determined that the participant has died, the site will use permissible local methods to obtain date and cause of death.

- If investigator's use of third-party representative to assist in the follow-up portion of the study has been included in the participant's informed consent, then the investigator may use a Sponsor retained third-party representative to assist site staff with obtaining participant's contact information or other public vital status data necessary to complete the follow-up portion of the study.
- The site staff and representative will consult publicly available sources, such as public health registries and databases, in order to obtain updated contact information.
- If after all attempts, the participant remains lost to follow-up, then the last known alive date as determined by the investigator should be reported and documented in the participant's medical records.

#### **8.4 Study Stopping Rules**

If, at any time during the study, the perceived risk/benefit changes, the BMS Medical Monitor and BMS Medical Surveillance Team Lead have the authority to determine whether or not the study should stop or be modified. Enrollment will be paused in the event of the following observations, confirmed by review of unblinded safety data:

- Mortality that is unusual for the study population as determined by the BMS team and Investigators
- 2 or more participants experience the same SAE and the event is not expected for the study population, is not expected for nivolumab, and is considered related to study treatment administration
- 1 participant has potential drug-induced liver injury (pDILI) as defined in [Section 9.2.8](#)

### **9. STUDY ASSESSMENTS AND PROCEDURES**

- Study procedures and timing are summarized in the Schedule of Activities (See [Section 2](#)).
- Protocol waivers or exemptions are not allowed.
- All immediate safety concerns must be discussed with the Sponsor immediately upon occurrence or awareness to determine if the participant should continue or discontinue treatment.
- Adherence to the study design requirements, including those specified in the Schedule of Activities, is essential and required for study conduct.
- All screening evaluations must be completed and reviewed to confirm that potential participants meet all eligibility criteria before randomization. The investigator will maintain a screening log to record details of all participants screened and to confirm eligibility or record reasons for screening failure, as applicable.
- Procedures conducted as part of the participant's routine clinical management (e.g., blood count) and obtained before signing of informed consent may be utilized for screening or baseline purposes provided the procedure meets the protocol-defined criteria and has been performed within the timeframe defined in the Schedule of Activities.

#### **9.1 Efficacy Assessments**

Exploratory efficacy assessments include the following:

- Organ failure will be assessed by collection of SOFA score during index hospitalization

- Organ support will be assessed by duration of mechanical ventilation, vasopressor use, or dialysis use separately during the index hospitalization
- Length of stay in the ICU and in the hospital during the index hospitalization will be assessed

### **9.1.1 Imaging Assessment for the Study**

Not applicable.

## **9.2 Adverse Events**

The definitions of an AE or serious adverse event (SAE) can be found in [Appendix 3](#).

AEs will be reported by the participant (or, when appropriate, by a caregiver, surrogate, or the participant's legally authorized representative).

The investigator and any designees are responsible for detecting, documenting, and reporting events that meet the definition of an AE or SAE and remain responsible for following up AEs that are serious, considered related to the study treatment or the study, or that caused the participant to discontinue before completing the study.

**Contacts for SAE reporting are specified in Appendix 3.**

### **9.2.1 Immune-mediated Adverse Events**

Immune-mediated AEs are AEs consistent with an immune-mediated mechanism or immune-mediated component for which non-inflammatory etiologies (e.g. infection or tumor progression) have been ruled out. Immune-mediated AEs can include events with an alternate etiology which were exacerbated by the induction of autoimmunity. Information supporting the assessment will be collected on the subject's case report form.

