#### 4. OBJECTIVES AND ENDPOINTS

**Table 4.-1: Objectives and Endpoints**

Objectives	Endpoints

Primary
 
 
To assess the safety and tolerability of a single dose of nivolumab 480 mg or 960 mg in participants with severe sepsis or septic shock
 
To assess the pharmacokinetics of BMS-936558 in participants with severe sepsis or septic shock
 
	
 
Incidence rates of SAEs, AEs, immune-mediated AEs, AEs leading to discontinuation, deaths, vital signs, ECG, or clinical laboratory abnormalities
 
Cmax, Cmin, Cavg, Tmax, AUC(0-T), CLT, Vd, T1/2.
 

Secondary
 
 
To assess receptor occupancy of nivolumab following single dose administration
 
To assess the effect of a single dose of nivolumab on monocyte HLA-DR expression and absolute lymphocyte count
 
To assess the immunogenicity of nivolumab following single dose administration
 
	
 
Receptor occupancy on T cells at baseline and after study treatment administration at planned sampling time points
 
Baseline and post-dosing assessments of mHLA-DR expression on monocytes, of absolute lymphocyte count
 
Number and percentage of participants with detectable anti-nivolumab antibodies at baseline and following single dose administration of nivolumab and the relationship with other outcome measures
 

[REDACTED]
	
[REDACTED]

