#### 2) Type of Participant and Target Disease Characteristics

- a) Men and women ages  $\geq 18$  years old
- b) Participant has documented OR suspected infection
  - i) Documented infection is infection confirmed with a microbiologic diagnosis
  - ii) Suspected infection is infection being treated with ongoing antimicrobial therapy at the time of study treatment administration
- c) Participant has the onset of severe sepsis or septic shock at least 24 hours prior to study treatment administration based on having at least 1 of the 3 organ dysfunction criteria below. Organ dysfunction must be new and thought to be due to sepsis.
  - i) Hypotension defined as the need for treatment with any vasopressor(s) for at least 6 hours to maintain a systolic pressure  $\geq 90$  mmHg or a mean arterial pressure  $\geq 70$  mmHg  
OR
  - ii) Acute respiratory failure defined as the need for invasive mechanical ventilation for at least 24 hours to support pulmonary function  
OR
  - iii) Acute kidney injury defined as creatinine  $> 2.0$  mg/dL (from a creatinine that was within the normal reference range prior to onset of sepsis) OR urine output  $< 0.5$  mL/kg/hr for  $> 2$  hours despite adequate fluid resuscitation. In the presence of pre-existing impairment of renal function (defined as a serum creatinine concentration  $> 2$  times the upper limit of the normal reference range prior to the onset of sepsis), the participant should meet 1 of the other 2 organ dysfunction criteria above.
- d) Participant has sepsis-associated immunosuppression based on an absolute lymphocyte count  $\leq 1100$  cells/ $\mu$ L on at least one assessment within the 96 hours prior to study treatment administration
- e) Participant is in an intensive care unit at the time of study treatment administration and, based on their medical condition, there are no plans to discharge from the ICU in the next 24 hours
- f) Participant Re-enrollment: This study permits the re-enrollment of a participant who has discontinued the study as a pre-treatment failure (ie, participant has not been randomized /has not been treated). If re-enrolled, the participant must be re-consented.

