### **9.2.2 Time Period and Frequency for Collecting AE and SAE Information**

The collection of nonserious AE information should begin at initiation of study treatment at the time points specified in the Schedule of Activities ([Section 2](#)) and for a minimum of 90 days following discontinuation of study treatment. Every adverse event must be assessed by the investigator with regard to whether it is considered immune-mediated. For events which are potentially immune-mediated, additional information will be collected on the participant's case report form. Nonserious AE information should also be collected from the start of a placebo lead-in period or other observational period intended to establish a baseline status for the participants.

Sections 5.6.1 and 5.6.2 in the Investigator Brochure (IB) represent the Reference Safety Information to determine expectedness of serious adverse events for expedited reporting. Following the participant's written consent to participate in the study, all SAEs, whether related or not related to study drug, must be collected, including those thought to be associated with protocol-specified procedures.

All SAEs must be collected that occur during the screening period and within 90 days of discontinuation of dosing.

- Medical occurrences that begin before the start of study treatment but after obtaining informed consent will be recorded on the appropriate section of the eCRF section.
- All SAEs will be recorded and reported to Sponsor or designee within 24 hours, as indicated in [Appendix 3](#).
- The investigator will submit any updated SAE data to the sponsor within 24 hours of this being available.

Investigators are not obligated to actively seek AEs or SAEs in former study participants. However, if the investigator learns of any SAE, including a death, at any time after a participant has been discharged from the study, and he/she considers the event reasonably related to the study treatment or study participation, the investigator must promptly notify the sponsor.

The method of evaluating, and assessing causality of AEs and SAEs and the procedures for completing and reporting/transmitting SAE reports are provided in [Appendix 3](#).

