4 ENDPOINTS

4.1 Primary Endpoint

The primary objective (to assess the safety and tolerability) will be measured by the incidence rates of AEs, SAEs, AEs leading to discontinuation, immune-mediated AEs, and deaths. In addition, clinical laboratory tests, vital signs, and ECGs will be summarized.

The primary objective (to assess the pharmacokinetics of BMS-936558) will be measured by the following PK endpoints.

C_{\max}	Peak nivolumab serum concentration
C_{\min}	Trough nivolumab serum concentration
C_{avg}	Average nivolumab serum concentration
T_{\max}	Time of maximum observed concentration
CLT	Total clearance
V_d	Volume of distribution
$T_{1/2}$	Half-life
$AUC(0-T)$	Area under the serum concentration-time curve from time zero to time of last quantifiable concentration

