- Drug-related adverse events on-treatment
- Adverse events on-treatment occurring in $\geq 5\%$ of subjects*
- Drug-related adverse events on-treatment occurring in $\geq 5\%$ of subjects*

* The 5% criterion cutoff refers to 5% in any column.

Two types of summaries are produced, one for subjects with grade 1-5 AEs and a second restricted to subjects with grade 3-4 & grade 5 AEs.

7.7.5 *Immune-Mediated Adverse Events*

In order to further characterize AEs of special clinical interest, an analysis of immune-mediated AEs (IMAEs) will be conducted. Immune-mediated AEs are specific events (or groups of PTs describing specific events) that include pneumonitis, diarrhea/colitis, hepatitis, nephritis/renal dysfunction, rash, endocrine (adrenal insufficiency, hypothyroidism/thyroiditis, hyperthyroidism, diabetes mellitus, and hypophysitis), and other specific events, considered potential immune-mediated events by investigator, that meet the definition summarized below:

- those occurring within 90 days of the dose,
- regardless of causality,
- treated with immune-modulating medication (of note, endocrine Adverse events such as adrenal insufficiency, hypothyroidism/thyroiditis, hyperthyroidism, diabetes mellitus, and hypophysitis are considered IMAEs regardless of immune-modulating medication use, since endocrine drug reactions are often managed without immune-modulating medication).

For the most recent immune-oncology studies, the data collection for IMAE was modified to also collect data on investigator assessment of potential IMAE including evidence of immune mediated etiology. For these studies, an additional criteria accounting for immune mediated etiology or immune mediated component is also to be considered:

- with no clear alternate etiology based on investigator assessment, or with an immune-mediated component

The list of MedDRA preferred terms used to identify Immune-Mediated adverse events is revisited quarterly and updated accordingly. The preferred terms used for the selection at the time of the database lock by categories will be provided.

IMAEs will be summarized by treatment group for each immune mediated category / PT using the 90-day safety window:

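### Protocol 9.2.1 asks that infection be ruled out before an AE counts as immune-mediated, although every participant has documented or suspected infection, and the rule is not reconciled with SAP 7.7.5

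*Protocol*

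**What the plan says.** Immune-mediated AE incidence belongs to the primary safety endpoint in both documents: Protocol Table 4.-1 has "Incidence rates of SAEs, AEs, immune-mediated AEs, AEs leading to discontinuation, deaths" and SAP 4.1 has "incidence rates of AEs, SAEs, AEs leading to discontinuation, immune-mediated AEs, and deaths".

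Protocol 9.2.1 limits the category to AEs consistent with an immune mechanism "for which non-inflammatory etiologies (e.g. infection or tumor progression) have been ruled out". Its next sentence adds an exception: "Immune-mediated AEs can include events with an alternate etiology which were exacerbated by the induction of autoimmunity". Protocol 9.2.2 makes the investigator the classifier: "Every adverse event must be assessed by the investigator with regard to whether it is considered immune-mediated". It asks for additional CRF information only on potentially immune-mediated events.

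Inclusion criterion 2b reads "Participant has documented OR suspected infection", and 2c requires new organ dysfunction attributed to sepsis.

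SAP 7.7.5 works from preferred-term groups within 90 days of the dose, "regardless of causality", and requires immune-modulating medication except for endocrine events. It then describes a further criterion for recent immune-oncology studies: "with no clear alternate etiology based on investigator assessment, or with an immune-mediated component". It plans three sets of summaries: all AEs on the term list with no medication or etiology filter, events where immune-modulating medication was initiated, and endocrine events.

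**The concern.** The 9.2.1 wording comes from oncology: tumor progression is one of its two examples, and infection is grouped with the non-inflammatory causes. In a cancer patient, infection is a competing explanation that can often be worked up and dismissed. Here it is the reason for enrollment. For a new lung, kidney, liver or gut event in a septic participant, it may be impossible either to exclude infection or to show that it is the whole cause. Protocol 9.2.1 gives no rule for that middle case, so an investigator who applies the exclusion clause strictly will leave the event unflagged.

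The flag matters beyond one table. It governs which events get the extra CRF detail in 9.2.2, and the definition sets the follow-up duty for non-serious immune-mediated AEs in 9.2.4. It is also the only protocol definition available for the immune-related AE tabulation in 10.3.1. An event dismissed as septic may lack the data needed to reclassify it later. This is the first trial of nivolumab in sepsis, and the immune-mediated AE count is one of the results that will inform whether further study is feasible.

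**Working it through.** **1. The plan's own figure.** Inputs from Protocol 10.1 and SAP 5: n = 15 per arm, true incidence p = 10%, stated probability of at least one occurrence 80%. Formula: P = 1 − (1 − p)^n = 1 − 0.9^15 = 0.794. The stated figure reproduces and is not in dispute.

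**2. One event under each rule.** Take an acute kidney injury that starts after dosing, where infection can be neither excluded nor shown to be the sole cause.

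| Rule | Counted? |
|---|---|
| Protocol 9.2.1, exclusion clause | No |
| Protocol 9.2.1, exception | Only if judged to be exacerbated by autoimmunity |
| Protocol 10.3.1 table | No definition other than 9.2.1, so it depends on the two rows above |
| SAP 7.7.5, unfiltered term table | Yes; acute kidney injury is listed in SAP Appendix 2 |
| SAP 7.7.5, medication table | Only if immune-modulating medication was initiated; the text does not exclude steroids begun for septic shock |
| SAP 7.7.5, etiology criterion | Yes if an immune-mediated component is judged present; whether the criterion applies to this trial is not stated |

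The same event can be in one table and out of another, and neither document says which table is the primary endpoint. New hypothyroidism, by contrast, is little affected: infection is no evident bar, and the SAP requires no medication for endocrine events.

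**3. Downward error (illustration).** Let s be the share of true immune-mediated AEs that survive the exclusion clause. The documents give no value, so s is an assumption. P = 1 − (1 − 0.10·s)^15.

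| s | Counted incidence | P(at least one of 15) |
|---|---|---|
| 1.0 | 10% | 79% |
| 0.9 | 9% | 76% |
| 0.75 | 7.5% | 69% |
| 0.5 | 5% | 54% |
| 0.25 | 2.5% | 32% |

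**4. Upward error (illustration).** Let f be the share of participants with a sepsis-caused event on the term list that is counted as immune-mediated, independent of true cases. This too is an assumption. With full capture, counted incidence is 1 − (1 − 0.10)(1 − f): 19% at f = 10%, 28% at f = 20%, 37% at f = 30%.

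**5. Break-even.** The two errors cancel when 1 − (1 − 0.10·s)(1 − f) = 0.10, that is f = (0.10 − 0.10·s)/(1 − 0.10·s). At s = 0.5, f = 0.05/0.95 = 5.3%. A small septic background would offset the loss of half the true cases, so the sign of the net error cannot be fixed from the documents.

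**The case against.** A reader might infer that the definition admits an event only after infection is excluded, and so drives the endpoint toward zero. The documents do not support that, for four reasons.

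- The clause concerns infection as the cause of the event, not infection in the participant. Thyroid, adrenal, pituitary, diabetes, rash and hypersensitivity terms in SAP Appendix 2 face no evident bar, and AE collection runs to Day 90.
- The second sentence of 9.2.1 admits events with another cause that autoimmunity exacerbated. It reads more naturally as an exception than as a contradiction.
- The SAP does not count by the 9.2.1 wording. Its etiology criterion is also met by an immune-mediated component alone, and one planned summary has no etiology or medication filter.
- All AEs are tabulated by system organ class and preferred term in any case, and sepsis-prone terms can raise the immune-mediated counts.

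All four points stand, and they rule out a claim of demonstrated bias toward zero. They do not remove the gap. The exception gives no guidance when the contribution of autoimmunity is uncertain. The unfiltered table is no substitute for a usable count: acute kidney injury and raised ALT, AST and bilirubin can come from sepsis itself, and with nivolumab in both arms there is no control to show the background rate. That sites will classify differently is plausible but not shown.

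**Conclusion.** The concern holds as a problem of definition and reconciliation. Protocol 9.2.1 invites under-classification of lung, kidney, liver and gut events and has no attribution rule suited to sepsis. SAP 7.7.5 uses a different definition, leaves open whether its etiology criterion applies, names no primary summary, and can err upward through sepsis-caused terms and septic-shock steroids. The investigator-assessed count may be too low and the SAP counts may be too high; the net direction is undetermined. No size can be derived from the documents: the fall from 79% to 54%, or to 32%, rests entirely on assumed values of s, and the upward figures rest on assumed values of f. The change should be made, because the count is part of a primary safety endpoint and the repair is cheap.

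**What to change.** - Reconcile Protocol 9.2.1 with SAP 7.7.5 under one named primary definition. State whether the SAP's etiology criterion applies to this trial.
- State in 9.2.1 that concurrent infection does not by itself disqualify an event.
- On the CRF page already planned for potentially immune-mediated events, record one of three levels: infection excluded as the cause; infection a possible contributor with an immune-mediated component suspected; infection a sufficient explanation.
- In SAP 7.7.5, report incidence by arm and total as a lower count (infection excluded) and an upper count (infection excluded or a contributor), next to the existing unfiltered preferred-term table.
- For the medication criterion, count immune-modulating medication only when it was started for the event, not for septic shock.

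The cost is protocol and SAP wording, one coded field and some extra table rows. The upper count will include some septic events and will look less favorable; the report should say so.
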